3.2.3 Rationale for Endpoints

3.2.3.1 Efficacy Endpoints

3.2.3.1.1 Primary Endpoint: Time to relapse (TTR)

The primary endpoint for this study is time to relapse (TTR). Patients with AML ≥ 60 years old in CR have a high relapse rate, which is the primary cause of death. The goal of PD-1 inhibition in AML is to harness the patient's immune system to eradicate submicroscopic disease and prevent relapse. As such, TTR was selected as the primary efficacy endpoint. TTR has been used as the endpoint in many similar clinical trials, and using this endpoint allow for valid comparison to historical controls. TTR is defined as survival in the absence of relapse, as defined by the Cheson criteria (see Section 12.3).

3.2.3.1.2 Second Efficacy Endpoints: Overall Survival

Overall survival is limited in AML, and the goal of all new therapy options in AML is to enhance overall survival. However, overall survival may be altered by subsequent therapy choices after relapse. As such, it will be measured as a secondary but not the primary endpoint.

3.2.3.2 Biomarker Research

Under normal physiologic conditions, check-point inhibition is a protective mechanism which prevents expansion of dangerous T cells capable of harming normal tissues. Tumors, including

PD-L1+ AML blasts, have corrupted this protective pathway by “bombarding” PD-1+ T cells, including anti-leukemia T cells, with the ligand overexpressed on AML blasts, thus inducing functional T-cell paralysis. The so called “exhaustion” of anti-leukemic T cells is, in fact, tumor-driven, chronically silencing activated T cells which are unable to mediate anti-leukemia activity in the tumor environment.

One objective of pembrolizumab therapy in AML is to rescue anti-leukemia T cells from blast-mediated chronic check-point inhibition by targeting PD-1 and allowing T cells to exercise anti-AML blast activity. Another objective is to decrease immune suppression mediated by regulatory T cells (Treg) which are increased in the frequency and activity in AML. [44] Treg, especially activated Treg present in patients with cancer, express PD-1 and it is likely that they are targeted by pembrolizumab via up-regulated antibody-mediated cellular cytotoxicity (ADCC). It is possible that this mechanism is responsible for, or contributes to, recovery of anti-leukemia T cell activity by removing Treg. As ADCC is largely mediated by Ab-armed activated NK cells, their functional recovery from check-point inhibition is an important consequence of pembrolizumab therapy. Exosomes produced by tumor cells or leukemic blasts are known to carry immunosuppressive cargo and to contribute to immune dysfunction of T cells and NK cells. We have recently observed that plasma-derived exosomes obtained from patients with AML carry PD-L1. We, therefore, expect that pembrolizumab would neutralize immunosuppressive exosomes.

In this study, we will measure recovery in the frequency/absolute numbers of activated immune cells and anti-leukemic functions of T cells after pembrolizumab therapy. We will measure anti-AML reactivity of T cells using autologous AML blast-derived antigens for ex vivo activation of T cells. We will monitor changes in the frequency and absolute numbers of Treg in the patients’ circulation. In addition, we will study levels and cargo of exosomes in the plasma. The hypothesis is that these immune parameters will be altered following pembrolizumab therapy and that change in the immune cell numbers and functions will provide insights into cellular mechanisms responsible for potential clinical responses observed in the proposed study.

Blood/tissue specimens will be saved at University of Pittsburgh Health Sciences Tissue Bank in the Department of Health Sciences Core Research where specimens will be coded using an Honest Broker. Correlative studies will be conducted in the laboratory of [name] at the University of Pittsburgh. Blood/tissue specimens will be labeled with study number not patient identifiers. Information linking these study numbers with the subject’s identity will be kept separate from the research records. Any breach in confidentiality will be reported to the IRB.

3.2.3.2.1 Quantitative study of T-cell subsets

Assay Description: 30ml in non-citrate tubes (heparinized) and 10ml in citrate tube(s) of peripheral blood will be obtained at the following time points: at diagnosis, prior to pembrolizumab initiation, prior to Cycles 2, 4, 8, 17 (± 1 treatment cycle) , and at disease progression or the end of 2 years of treatment, whichever comes first. We will perform immunofluorescence staining and multiparameter flow cytometry to evaluate expression of PD-L1 and PD-1 on blasts and effector cells and changes in the patients’ lymphocyte subsets and the expression of their surface receptors at these specific time points. The conjugated monoclonal antibodies CD 45, 3, 4, 8, 25, 39, 69, 56, FOXP3 and NKp46 will be used in

combinations to evaluate Total CD8+ Tcells and activated T-cells, total and activated CD4+ Tcells, total and activated NK cells and Treg.

Assay Performance: The frequency of the aforementioned T-cell and NK cell subsets in healthy donors is well documented. On the other hand, the frequency of these T and NK cells subset in AML patients is incompletely documented. PBMCs from 15 age-matched healthy donors will be studied as control group. A sample that is positive for above markers will be used as the positive control for the staining as well. Isotype controls for all Abs will be used. Flow cytometry is an established methodology with well-defined accuracy and precision.

Data interpretation and considerations: The proportions and absolute numbers of total and activated (CD69+/ CD25+) CD8+ T-cells, total and activated CD4+ Tcells, and CD3-CD56+ NK cells in AML patients at diagnosis and prior to pembrolizumab will be compared to values obtained with PBMC of healthy donors. These values in AML patients are expected to be lower than the established normal, suggesting the presence of T-cell suppression and/or apoptosis. Following pembrolizumab therapy, these values are expected to increase. Tregs (CD4+CD39+FOXP3+ and CD4+FOXP3+CD25+PD-1+) are expected to be elevated in frequency and absolute numbers in AML patients prior to pembrolizumab therapy. We expect Treg percentages/absolute numbers to decrease after pembrolizumab therapy based on the hypothesis that this Ab targets PD-1+ Treg and eliminates them. Expression of PD-1 is expected to decrease after therapy. This would suggest that pembrolizumab restores anti-leukemia immune responses not only by removing the checkpoint blockade and allowing for immune cell activation but also by removing Treg-mediated suppression.

3.2.3.2.2 T-cell expression of IFN- γ and Granzyme B/Perforin in T-cells stimulated *in vivo* with autologous AML blast-derived antigens

Assay Description: Cryopreserved PBMCs will be thawed and washed. Autologous AML blasts will be separated from PBMCs at diagnosis, cryopreserved and stored. Just prior to the assay, AML blasts will be repeatedly frozen/thawed to solubilize the potentially relevant antigens. The protein content of the lysates will be determined. Lysates of autologous AML blasts will be used for *in vitro* stimulation of lymphocytes in PBMC. Antigen-presenting cells (APC) in PBMCs will be able to present antigens in the lysate to immune cells. Stimulation may be antigen-specific via the Tcell receptor (TCR) on cognate T cells or non-specific via TLRs or other receptors on immune cells responding to antigens in the lysate. IFN- γ expression by CD8+ T-cells and granzyme B (GrB) and perforin expression by CD8 T-cells and NK cells will be measured as previously described. [54] Briefly, lysates of autologous blasts will be added to PBMC at 3 different concentrations and incubated for 18 h. Cells harvested from these cultures will be incubated with mAbs specific for surface markers (CD3, CD4, CD8, CD56), fixed with 4% paraformaldehyde in phosphate buffered saline (PBS) for 20 min at room temperature, washed once with PBS containing 0.5% bovine serum albumen (BSE) and 2 nM ethylene diamine triacetic acid, permeabilized with PBS containing 0.5% BSA and 0.1% saponin, washed and stained with pre-titrated anti-GrB-PE, anti-perforin-FITC, and IFN- γ -PE. Flow cytometry will be performed immediately on a Beckman Coulter equipped with Expo32 software. Percentages of IFN- γ -positive cells among CD8+ T cells and GrB/Perforin-positive CD8+ T cells and CD3-CD56+NK cells will be determined.

Assay Performance: This is a two-step assay selected for monitoring of immune cell (T and NK cell) responses to a mix of blast-derived antigens. [54] This is an autologous system, with PBMC serving as APC. The assay can be readily adapted to serial monitoring. PBMC and autologous lysates will be cryopreserved and thawed for culture. Serially-collected specimens of each patient (as described in Section 4.2.3.2.1) will be batched and tested in one assay to avoid inter-assay variability. Culture controls set in parallel with patients' samples will be PBMCs of a normal donor (cryopreserved in bulk to supply the same control for all patients' cultures) stimulated with anti-CD3/CD28 Abs. Also, PBMCs of each evaluated AML patient will be stimulated with anti-CD3/CD28 Abs to serve as control for the ability to respond to TCR-mediated signals. 18h activation was previously shown to be a sufficient time period for induction of intra-cytoplasmic cytokines or GrB/perforin expression. [54] Multicolor flow cytometry assessments after cell permeabilization and staining with labeled antibodies to T and NK cell surface markers and the relevant cytokines are routinely performed on an instrument which is calibrated daily. The SOP for the assay is on file.

Data interpretation and considerations: This assay should be able to inform us about the ability of AML patients' immune cells to respond by cytokine or GrB/perforin expression to external stimulatory signals. [55] We expect from 10 to 15% of CD8+T cells of a normal donor to respond to activation with anti-CD3/CD28 Abs by up-regulating expression of these mediators. We expect to see a much lower frequency of responsive T-cells in AML patients. Only a small percentage of immune cells in AML patients (2-4%) are expected to respond to AML blast-derived lysates. Cells of normal donors (used as controls) are likely to respond but this will reflect alloantigen- rather than AML antigen-driven response. In patients receiving pembrolizumab, we expect to see recovery of T- cell responses to anti-CD3/CD28 Abs and of T and NK cell responses to antigens in AML blast-derived lysates by up-regulated expression of either IFN-g or GrB/perforin or both.

The proportions/ absolute numbers of CD8+ T cells and NK cells expressing IFN- γ as well as CD8+ T-cells and NK cells expressing GrB and Perforin will be evaluated at diagnosis and just prior to starting pembrolizumab therapy and will be compared to the proportions/absolute numbers of positive cells at pre-determined intervals after pembrolizumab treatment. The numbers of CD8+ T cells and NK cells expressing IFN- γ , GrB and/or perforins are expected to increase from values at diagnosis and those prior to pembrolizumab treatment. This increase would suggest recovery of normal immune responses to general stimulatory signals and to AML blast-derived signals, providing evidence for the effect of pembrolizumab on AML blast-reactive T-cells and NK cells through elimination of the checkpoint blockade and/or potentially also through ADCC directed at Treg.

3.2.3.2.3: Effects of pembrolizumab on functions and levels of exosomes

Exosomes are small (30-150nm) vesicles secreted by all cell types and present in all body fluids. [56] While exosome secretion occurs under physiologic conditions, tumor cells are avid exosome producers. In AML, blast-derived exosomes carry an immunosuppressive cargo. Furthermore, plasma exosomes in patients with newly diagnosed with AML prior to any therapy had higher levels of exosomes (in μg protein/mL plasma) compared to normal donors [57]. *Ex vivo*, exosomes decrease NK-cell cytotoxicity and down-regulate NKG2D expression in normal NK cells. More recently, we have shown elevated levels of exosomes in AML patients that are in complete remission and that these exosomes contain PD1 and PD-L1. [58]

We hypothesize that the use of pembrolizumab will affect the immunosuppressive activity of exosomes.

Assay Description: Exosomes will be isolated from the plasma of AML patients using differential centrifugation, ultrafiltration and size-exclusion chromatography on mini-Sepharose 2a columns. Using Western blotting, we will identify the exosomal cargo, including PD1, PD-L1, TGF- β 1 and CD39 and CD73. To study immune suppression mediated by exosomes, AutoMACs-isolated normal NK or T cells will be co-incubated with exosomes isolated at the time of enrollment prior to pembrolizumab therapy. The levels of exosomes and the effects on the function of the immune cells will be monitored serially at diagnosis, prior to pembrolizumab initiation, at 1, 3, 6, 12, and 24 months post initiation of pembrolizumab .

Data interpretation and considerations: The hypothesis is that suppression of normal NK or T cells by AML exosomes and concomitant activation of Treg reverse with the use of pembrolizumab. Silencing of the negative signals should diminish or ablate exosome-mediated immune suppression and restore immune cell functions.

4.0 METHODOLOGY

4.1 Entry Criteria

4.1.1 Diagnosis/Condition for Entry into the Trial

Subject eligible for entry into the trial must have a diagnosis of non-M3 AML and currently be in first CR/CRi (see Appendix I for response criteria). Patients should receive 2-4 cycles of consolidation, provided that the last dose of either induction chemotherapy or consolidation chemotherapy falls within 3 months prior to enrollment in this trial. A patient receiving less than 2 of consolidation therapy is eligible only if they are deemed intolerant to consolidation therapy by the treating physician.

4.1.2 Subject Inclusion Criteria

In order to be eligible for participation in this trial, the subject must:

1. Be willing and able to provide written informed consent for the trial.
2. Be ≥ 60 years of age on day of signing informed consent.
3. Have a newly diagnosed AML, based on World Health Organization criteria [59], currently in 1st CR/CRi (see 12.3 for definition of CR/CRi) on a bone marrow biopsy performed within 4 weeks of study enrollment.
4. Have received the last dose of induction or consolidation chemotherapy within 3 months of enrollment.
5. Have a performance status of ≤ 1 on the ECOG Performance Scale.

- Demonstrate adequate organ function as defined in Table 1, with all screening labs performed within 10 days of treatment initiation.

Table 1: Adequate Organ Function Laboratory Values

| System | Laboratory Value |
|---|---|
| Hematological | |
| Absolute neutrophil count (ANC) | ≥1,000 /mcL with no growth factor support in the previous 3 weeks |
| Platelets | ≥50,000 / mcL (transfusion independent) |
| Hemoglobin | ≥9 g/dL or ≥5.6 mmol/L |
| Renal | |
| Serum creatinine OR Measured or calculated ^a creatinine clearance (GFR can also be used in place of creatinine or CrCl) | ≤1.5 X upper limit of normal (ULN) OR ≥60 mL/min for subject with creatinine levels > 1.5 X institutional ULN |
| Hepatic | |
| Serum total bilirubin | ≤ 1.5 X ULN OR Direct bilirubin ≤ ULN for subjects with total bilirubin levels > 1.5 ULN |
| AST (SGOT) and ALT (SGPT) | ≤ 2.5 X ULN |
| Coagulation | |
| International Normalized Ratio (INR) or Prothrombin Time (PT) | ≤1.5 X ULN unless subject is receiving anticoagulant therapy as long as PT or PTT is within therapeutic range of intended use of anticoagulants |
| Activated Partial Thromboplastin Time (aPTT) | ≤1.5 X ULN unless subject is receiving anticoagulant therapy as long as PT or PTT is within therapeutic range of intended use of anticoagulants |
| ^a Creatinine clearance should be calculated per institutional standard. | |

- Transfusion independent (no red blood cell or platelet transfusions in the preceding 2 weeks of screening).
- Female subject of childbearing potential require a negative pregnancy test within 72 hours prior to receiving the first dose of study medication. If the urine test is positive or cannot be confirmed as negative, a serum pregnancy test will be required.
- Female subjects of childbearing potential must be willing to use 2 methods of birth control or be surgically sterile, or abstain from heterosexual activity for the course of the study through 120 days after the last dose of study medication (Reference Section 5.7.2). Subjects of childbearing potential are those who have not been surgically sterilized or have not been free from menses for > 1 year.
- Male subjects must agree to use an adequate method of contraception starting with the first dose of study therapy through 120 days after the last dose of study therapy.

4.1.3 Subject Exclusion Criteria

The subject must be excluded from participating in the trial if the subject:

- Has a diagnosis of Acute Promyelocytic Leukemia (APL) as defined by the World Health Organization. [59]

2. Eligible and willing to proceed with an allogeneic stem cell transplant with an acceptable stem cell donor
3. Has favorable risk AML as defined by the presence of isolated t(8;21) or inv(16) or t(16;16)(p13.1;q22) on a standard karyotype or mutated NPM1 with concurrent wild-type FLT3 on molecular testing.
4. Is currently participating in or has participated in a study of an investigational agent or using an investigational device within 4 weeks of the first dose of treatment.
5. Has a diagnosis of immunodeficiency or is receiving systemic steroid therapy or any other form of immunosuppressive therapy within 7 days prior to the first dose of trial treatment.
6. Has had a prior monoclonal antibody within 4 weeks prior to study Day 1 or who has not recovered (i.e., \leq Grade 1 or at baseline) from adverse events due to agents administered more than 4 weeks earlier.
7. Has had prior chemotherapy, targeted small molecule therapy, or radiation therapy within 2 weeks prior to study Day 1 or who has not recovered (i.e., \leq Grade 1 or at baseline) from adverse events due to a previously administered agent.
 - Note: Subjects with \leq Grade 2 neuropathy are an exception to this criterion and qualify for the study.
 - Note: If subject received major surgery, they must have recovered adequately from the toxicity and/or complications from the intervention prior to starting therapy.
8. Has a known additional malignancy that is progressing or requires active treatment. Exceptions include basal cell carcinoma of the skin, squamous cell carcinoma of the skin, or in situ cervical cancer that has undergone potentially curative therapy.
9. Has known active central nervous system (CNS) involvement. Subjects with previously treated CNS disease may participate provided they are stable (without evidence of CNS leukemia at the time of screening and any neurologic symptoms have returned to baseline) and are not using steroids for at least 7 days prior to trial treatment.
10. Has an active automimmune disease requiring systemic treatment within the past 3 months or a documented history of clinically severe autoimmune disease, or a syndrome that requires systemic steroids or immunosuppressive agents. Subjects with vitiligo or resolved childhood asthma/atopy are an exception to this rule, and are eligible. Subjects that require intermittent use of bronchodilators or local steroid injections would not be excluded from the study. Subjects with hypothyroidism stable on hormone replacement or Sjogren's syndrome will not be excluded from the study.

11. Has a history of (non-infectious) pneumonitis that required steroids or current pneumonitis.
12. Has an uncontrolled, life-threatening active infection.
13. Has a history or current evidence of any condition, therapy, or laboratory abnormality that might confound the results of the trial, interfere with the subject's participation for the full duration of the trial, or is not in the best interest of the subject to participate, in the opinion of the treating investigator.
14. Has known psychiatric or substance abuse disorders that would interfere with cooperation with the requirements of the trial.
15. Is pregnant or breastfeeding or expecting to conceive or father children within the projected duration of the trial, starting with the pre-screening or screening visit through 120 days after the last dose of trial treatment.
16. Has received prior therapy with an anti-PD-1, anti-PD-L1, anti-PD-L2, anti-CD137, or anti-Cytotoxic T-lymphocyte-associated antigen-4 (CTLA-4) antibody (including ipilimumab or any other antibody or drug specifically targeting T-cell co-stimulation or checkpoint pathways).
17. Has a known history of Human Immunodeficiency Virus (HIV) (HIV 1/2 antibodies).
18. Has known active Hepatitis B (e.g., HBsAg reactive) or Hepatitis C (e.g., HCV RNA [qualitative] is detected).
19. Has received a live vaccine within 30 days prior to the first dose of trial treatment.

4.2 Trial Treatments

The treatment to be used in this trial is outlined below in Table 2.

Table 2: Trial Treatment

| Drug | Dose | Dose Frequency | Route of Administration | Regimen/Treatment Period | Use |
|---|--------|----------------|-------------------------|--------------------------|--------------|
| pembrolizumab | 200 mg | Every 3 weeks | IV infusion | Up to 2 years | Experimental |
| The pembrolizumab dosing interval may be increased due to toxicity as described in Section 4.2.1.2. | | | | | |

Trial treatment should begin on the day of treatment assignment, or as close as possible to the day at which treatment is assignment. Treatment must occur within 10 days of official enrollment, or all screening tests must be repeated.

4.2.1 Dose Selection/Modification

4.2.1.1 Dose Selection

The rationale for selection of doses to be used in this trial is provided in Section 4.0 – Background and Rationale.

Details on preparation and administration of Pembrolizumab are provided in the Pharmacy Manual.

4.2.1.2 Dose Modification

Adverse events (both non-serious and serious) associated with Pembrolizumab exposure may represent an immunologic etiology. These adverse events may occur shortly after the first dose or several months after the last dose of treatment. Adverse experiences will be graded and recorded throughout the study and during the follow-up period according to NCI CTCAE Version 4.0. Pembrolizumab must be withheld for drug-related toxicities and severe or life-threatening drug-related AEs as per Table 3 below. See Section 4.6.1 and Events of Clinical Interest Guidance Document for supportive care guidelines, including use of corticosteroids.

**Table 3
Dose Modification Guidelines for Drug-Related Adverse Events**

| Toxicity | Hold Treatment For Grade | Timing for Restarting Treatment | Discontinue Subject |
|----------------------------------|--------------------------|---------------------------------|--|
| Diarrhea/Colitis | 2-3 | Toxicity resolves to Grade 0-1. | Toxicity does not resolve within 12 weeks of last dose or inability to reduce corticosteroid to 10 mg or less of prednisone or equivalent per day within 12 weeks. |
| | 4 | Permanently discontinue | Permanently discontinue |
| AST, ALT, or Increased Bilirubin | 2 | Toxicity resolves to Grade 0-1 | Toxicity does not resolve within 12 weeks of last dose. |

| Toxicity | Hold Treatment For Grade | Timing for Restarting Treatment | Discontinue Subject |
|---|--------------------------|---|--|
| | 3-4 | Permanently discontinue | Permanently discontinue |
| Type 1 diabetes mellitus (if new onset) or Hyperglycemia | T1DM or 3-4 | Hold Pembrolizumab for new onset Type 1 diabetes mellitus or Grade 3-4 hyperglycemia associated with evidence of beta cell failure. | Resume Pembrolizumab when patients are clinically and metabolically stable. |
| Hypophysitis | 2-3 | Toxicity resolves to Grade 0-1 | Toxicity does not resolve within 12 weeks of last dose or inability to reduce corticosteroid to 10 mg or less of prednisone or equivalent per day within 12 weeks. |
| | 4 | Permanently discontinue | Permanently discontinue |
| Hyperthyroidism | 3 | Toxicity resolves to Grade 0-1 | Toxicity does not resolve within 12 weeks of last dose or inability to reduce corticosteroid to 10 mg or less of prednisone or equivalent per day within 12 weeks. |
| | 4 | Permanently discontinue | Permanently discontinue |
| Hypothyroidism | 2-4 | Therapy with Pembrolizumab can be continued while treatment for the thyroid disorder is instituted | Therapy with Pembrolizumab can be continued while treatment for the thyroid disorder is instituted. |
| Infusion Reaction | 3-4 | Permanently discontinue | Permanently discontinue |
| Pneumonitis | 2 | Toxicity resolves to Grade 0-1 | Toxicity does not resolve within 12 weeks of last dose or inability to reduce corticosteroid to 10 mg or less of prednisone or equivalent per day within 12 weeks. |
| | 3-4 | Permanently discontinue | Permanently discontinue |
| Renal Failure or Nephritis | 2 | Toxicity resolves to Grade 0-1 | Toxicity does not resolve within 12 weeks of last dose or inability to reduce corticosteroid to 10 mg or less of prednisone or equivalent per day within 12 weeks. |
| | 3-4 | Permanently discontinue | Permanently discontinue |
| All Other Drug-Related Toxicity ¹ | 3 or Severe | Toxicity resolves to Grade 0-1 | Toxicity does not resolve within 12 weeks of last dose or inability to reduce corticosteroid to 10 mg or less of prednisone or equivalent per day within 12 weeks. |
| | 4 | Permanently discontinue | Permanently discontinue |
| Note: Permanently discontinue for any severe or Grade 3 drug-related AE that recurs or any life-threatening event. | | | |
| ¹ Patients with intolerable or persistent Grade 2 drug-related AE may hold study medication at physician discretion. Permanently discontinue study drug for persistent Grade 2 adverse reactions for which treatment with study drug has been held, that do not recover to Grade 0-1 within 12 weeks of the last dose. | | | |

Dosing interruptions are permitted in the case of medical / surgical events or logistical reasons not related to study therapy (e.g., elective surgery, unrelated medical events, patient vacation, and/or holidays). Subjects should be placed back on study therapy within 3 weeks of the scheduled interruption, unless otherwise discussed with the Investigator. The reason for interruption should be documented in the patient's study record.

Subjects with a history of AML who undergo induction therapy may have intermittent thrombocytopenia or neutropenia. This may be due to relapse of AML but could also be due to viral infection, a medication effect, or an unexplained by transient etiology. Thrombocytopenia and neutropenia are not commonly (>10%) experienced adverse event with pembrolizumab in other clinical studies in solid tumors (Investigator's Brochure). As such, pembrolizumab treatment should not be withheld for a platelet count of $\geq 30,000/\text{mcL}$ or an absolute neutrophil count of $\geq 500/\text{mcL}$ unless the investigator feels that disease assessment is warranted. However, if platelet count is $< 30,000/\text{mcL}$ or ANC is $< 500/\text{mcL}$, pembrolizumab therapy should be held and the etiology of the thrombocytopenia evaluated. If platelets increase to $\geq 30,000/\text{mcL}$ and ANC to $\geq 500/\text{mcL}$ within 3 weeks, pembrolizumab may be restarted at the current dose. If a subject develops febrile or prolonged neutropenia which requires growth

factor support at the discretion of the investigator, pembrolizumab should be permanently discontinued.

The dose may be held based on assessment of the patient at the time of the scheduled dose. If the dose is held, the patient will be reassessed weekly (or more frequently if clinically indicated) and dosing will be restarted at the discretion of the principal investigator.

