6.2.4 Evaluating Adverse Events

An investigator who is a qualified physician will evaluate all adverse events according to the NCI Common Terminology for Adverse Events (CTCAE), version 4.0. Any adverse event which changes CTCAE grade over the course of a given episode will have each change of grade recorded on the adverse event case report forms/worksheets.

All adverse events regardless of CTCAE grade must also be evaluated for seriousness.

Table 10: Evaluating Adverse Events

An investigator who is a qualified physician, will evaluate all adverse events as to:

| | | | | | | | | |
|----------------------------------|--|---|-----------------|--|--------------------|---|---------------------|---|
| V4.0 CTCAE Grading | Grade 1 | Mild; asymptomatic or mild symptoms; clinical or diagnostic observations only; intervention not indicated. | | | | | | |
| | Grade 2 | Moderate; minimal, local or noninvasive intervention indicated; limiting age-appropriate instrumental ADL. | | | | | | |
| | Grade 3 | Severe or medically significant but not immediately life-threatening; hospitalization or prolongation or hospitalization indicated; disabling; limiting self-care ADL. | | | | | | |
| | Grade 4 | Life threatening consequences; urgent intervention indicated. | | | | | | |
| | Grade 5 | Death related to AE | | | | | | |

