7.3 Stopping Rule for Excess Toxicity

The table displays the stopping rule for excessive toxicity. Excessive toxicity is defined as any drug-related toxicity that results in withholding or discontinuation of pembrolizumab. Additionally, any unexpected grade 3-4 AEs will be defined as excessive toxicity.”

| # Patients | #Toxicities |
|------------|-------------|
| 5 | 3 |
| 10 | 4 |
| 15 | 5 |
| 20 | 7 |
| 25 | 8 |
| 30 | 9 |
| 35 | 10 |

[figure not shown]
The trial is suspended if the number of toxicities is greater than or equal to the number in the second column. For instance, if 5 out of the first 15 patients experience severe toxicity,

the trial is suspended if the number of toxicities is greater than or equal to the number in the second column. For instance, if 5 out of the first 15 patients experience severe toxicity, the trial is suspended.

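### Section 4.2.1.2 gives incompatible continue, resume and discontinue instructions for Grade 4 endocrine events and drug-related cytopenias, and does not say which governs

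*Combined protocol and SAP*

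**What the plan says.** All the dosing rules at issue are in section 4.2.1.2 (Dose Modification).

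- The opening text makes Table 3 binding: "Pembrolizumab must be withheld for drug-related toxicities and severe or life-threatening drug-related AEs as per Table 3 below".
- The Table 3 note adds: "Permanently discontinue for any severe or Grade 3 drug-related AE that recurs or any life-threatening event". Table 10 in section 6.2.4 describes Grade 4 as "Life threatening consequences; urgent intervention indicated".
- The Type 1 diabetes / hyperglycemia row holds treatment for new-onset disease or Grade 3-4 hyperglycemia. Then, in the column meant for discontinuation, it says "Resume Pembrolizumab when patients are clinically and metabolically stable".
- The hypothyroidism row lists Grades 2-4 in the column of grades to hold for, but its text is "Therapy with Pembrolizumab can be continued while treatment for the thyroid disorder is instituted".
- The row "All Other Drug-Related Toxicity" holds Grade 3 until the event is Grade 0-1 and permanently discontinues for Grade 4.
- A paragraph after the table deals with thrombocytopenia and neutropenia. It names relapse, viral infection, a medication effect and unexplained transient causes. It says "pembrolizumab treatment should not be withheld for a platelet count of" at least 30,000/mcL or an ANC of at least 500/mcL, unless the investigator wants a disease assessment. Below either value, treatment is held and the cause evaluated. Restart is permitted if both counts regain those values within 3 weeks. Permanent discontinuation is reserved for febrile or prolonged neutropenia that needs growth factor.

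The stopping rule in section 7.3 uses these actions as its event: "Excessive toxicity is defined as any drug-related toxicity that results in withholding or discontinuation of pembrolizumab". It then adds unexpected Grade 3-4 adverse events as a second route.

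**The concern.** A drug-related event can fall under two of these provisions at once, and the section does not say which one prevails. For the same severe event, a physician could follow the protocol and continue or resume treatment, or follow it and stop treatment for good. The main stake is patient safety and uniform conduct. A secondary stake is the toxicity stopping rule: its event is defined partly by what was done to dosing, so an ambiguous dosing rule can make the event ambiguous too.

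**Working it through.** **Step 1. The instructions side by side.**

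| Drug-related event | Instruction A | Instruction B | Needs an unprinted figure? |
|---|---|---|---|
| 1. Grade 4 hyperglycemia | Row: hold, then resume when stable | Note with Table 10: permanently discontinue | No |
| 2. Grade 4 hypothyroidism | Row: may continue | Note with Table 10: permanently discontinue | No |
| 3. Cytopenia below 30,000 or 500, Grade 4 | Paragraph: hold; restart permitted on count recovery | Catch-all row: permanently discontinue | No |
| 4. Cytopenia at or above 30,000 or 500 | Paragraph: do not withhold | Catch-all row: hold, if Grade 3 | Yes |

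Conflict 3 needs no exact cut-off. The paragraph's lower branch has no floor, so it takes in the most severe counts. It is enough that some count below 30,000 or 500 is Grade 4.

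**Step 2. The assumption behind conflict 4.** Section 11.2 adopts CTCAE v4.0 without printing count limits. Let U be the count below which a cytopenia is Grade 3 or worse. The conflict band is then 30,000 to U for platelets and 500 to U for ANC.

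- If U is 30,000 or lower (platelets), or 500 or lower (ANC), the band is empty and there is no conflict.
- If U is 50,000 and 1,000 (assumed), the bands are 30,000 to below 50,000 (width 20,000) and 500 to below 1,000 (width 500).
- Intermediate values of U give intermediate widths.

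**Step 3. Which conflicts can change the section 7.3 count.** A hold and a discontinuation each count as one toxicity. Conflicts 1 and 3 involve a hold under either reading, so they change the count by zero. Conflicts 2 and 4 set no action against an action, so they can change it by one per patient, unless the event is counted anyway as an unexpected Grade 3-4 event. Section 7.3 does not define unexpected.

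**Step 4. The plan's boundary.** Section 7.4 stops if P(p > 0.2 | Beta(2+y, 8+n-y)) > 0.8. The smallest such y reproduces the printed table at every look.

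| n | Boundary y | Posterior at y | Posterior at y-1 |
|---|---|---|---|
| 5 | 3 | 0.870 | 0.698 |
| 10 | 4 | 0.837 | 0.673 |
| 15 | 5 | 0.811 | 0.656 |
| 20 | 7 | 0.892 | 0.790 |
| 25 | 8 | 0.875 | 0.773 |
| 30 | 9 | 0.859 | 0.759 |
| 35 | 10 | 0.846 | 0.746 |

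**Step 5. Illustration of size.** Let b be the rate of undisputed countable toxicity. Let q be the chance of an event of type 2 or 4, taken as independent of the rest. Both are assumed. If disputed events are counted, the rate is p = 1 - (1-b)(1-q); if not, it is b. The chance of suspension is the exact binomial probability of reaching the printed boundary at any of the seven looks.

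| b | q | p | P(suspend) |
|---|---|---|---|
| 0.10 | 0 | 0.10 | 0.025 |
| 0.10 | 0.025 | 0.1225 | 0.053 |
| 0.10 | 0.05 | 0.145 | 0.096 |
| 0.10 | 0.10 | 0.19 | 0.24 |
| 0.20 | 0 | 0.20 | 0.28 |
| 0.20 | 0.025 | 0.22 | 0.37 |
| 0.20 | 0.05 | 0.24 | 0.47 |
| 0.20 | 0.10 | 0.28 | 0.66 |

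The documents do not give q. Section 3.1.2 reports immune-related hypothyroidism in 2.7% of melanoma patients. If that rate carried over, 40 x 0.027 = 1.1 patients would be expected with it, and Grade 4 cases can be no more than that. The larger values of q would therefore have to come mainly from conflict 4, which is conditional.

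These probabilities use the printed table. Section 7.4 states different operating characteristics at a true rate of 0.4 (stopping probability 0.5, expected accrual 28) from those the table gives (0.96 and 12.9). That is a separate matter and nothing here depends on it.

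**The case against.** The best defence is that specific text overrides general text. The endocrine rows are more specific than the note beneath them. The cytopenia paragraph follows Table 3, concerns AML patients and gives its reason. This is a natural reading, but the protocol does not state it. The paragraph allows for a medication effect, while the opening text makes Table 3 mandatory for drug-related events.

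Other points carry some weight:

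- Below the thresholds the paragraph requires the cause to be evaluated and says only that treatment may be restarted. A later paragraph leaves restart after a hold to the principal investigator of a single-center trial. This narrows variation between physicians over restart. It does not say what follows if the cause is judged to be pembrolizumab, and it does not reach conflict 2, where nothing is held.
- The paragraph has its own permanent-discontinuation branch for neutropenia needing growth factor. That covers part of conflict 3. It does not cover thrombocytopenia, or neutropenia managed without growth factor.
- Table 10's seriousness row uses a narrower sense of life-threatening (immediate risk of death) than its Grade 4 line, and the note does not say which it means. On the narrower sense some Grade 4 events escape the note. An event that meets both senses does not.
- Within the hypothyroidism row both action columns agree, so the grades under the hold column may be only a layout fault. The clash with the note remains.

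**Conclusion.** The point holds as a patient-safety inconsistency. Conflicts 1 to 3 rest on the documents alone, given that the note is read with Table 10 and the event is judged drug-related. Conflict 4 also needs Grade 3 to extend above 30,000 platelets or an ANC of 500, which the documents do not show.

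Three stronger readings are tempting but not supported:

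- A reader might infer that the stopping rule is distorted by every one of these conflicts. Two of the four leave the count unchanged, and the unexpected-event clause may capture the other two. That one patient can decide suspension is true of any boundary and does not measure this defect. The probabilities above only illustrate assumed rates.
- A reader might infer that patients who enter at the Table 1 minima (platelets 50,000, ANC 1,000) could never meet Table 3's Grade 0-1 restart condition. That depends on the same unprinted cut-offs, and where to set a restart level is a clinical decision.
- A reader might infer that section 4.6.1, which names ketoacidosis, extends the resume instruction to it. That passage is supportive-care guidance and is silent on resuming.

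No effect on the primary efficacy analysis is shown.

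**What to change.** 1. Reconcile the Table 3 note with the Type 1 diabetes / hyperglycemia row and the hypothyroidism row, and put each instruction in the column that matches its meaning.
2. Reconcile the cytopenia paragraph with Table 3's catch-all row: state which governs when a cytopenia is judged drug-related and which when it is not.
3. In section 7.3, count events under the reconciled rule, and say whether the events in conflicts 2 and 4 fall within the unexpected Grade 3-4 clause.

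Which clinical rule to adopt is the sponsor's decision. The cost is protocol wording only, with no added patients, visits or tests.
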